Disclosures. Separate from this work, [name] has received grant and research support unrelated to this study from the American Psychological Foundation, the Klingenstein Third Generation Foundation, the Center on the Developing Child at Harvard University, Limbix Health, Inc., and the National Institutes of Health. [name] and [name] are under contract with New Harbinger Publications to co-author a therapy workbook for adolescents. [name] receives research support from a Stony Brook University Graduate Council Fellowship. [name] has received grant and research funding unrelated to this study from the National Institute of Health, HRSA, Agency for Healthcare Research and Quality, Centers for Disease Control, Slomo and Cindy Silvan Foundation, New York State Office for People with Developmental Disabilities, New York State Department of Health. The Commonwealth of Pennsylvania, Department of Public Welfare, American Lung Association, Robert Wood Johnson Foundation. Anne E. Dyson Foundation, David E. Rogers Foundation, Arnold P. Gold Foundation, and The Pew Charitable Trusts. The authors report no additional financial conflicts.

**Promoting treatment access following pediatric primary care depression screening:
Randomized trial of web-based, single-session interventions for parents and youths**

Stage 1 Registered Report

Study Synopsis

Introduction Summary. Major depression in youth is a serious psychiatric illness with extensive acute and chronic morbidity and mortality.¹ In 2018, the American Academy of Pediatrics released updated practice guidelines promoting screening of youth depression in primary care (PC) clinics across the country, representing a critical step towards increasing early depression detection.² However, the challenge of bridging screening with service access remains. Even when diagnosed by PC providers, <50% of youth with elevated depressive symptoms access treatment of any kind.² Thus, there is a need for interventions that are more feasible for youths and parents to access and complete—and that may strengthen parents’ likelihood of pursuing future, longer-term services for their child.

Single-session interventions (SSIs) may offer a promising path toward these goals. SSIs include core elements of comprehensive, evidence-based treatments, but their brevity makes them easier to disseminate beyond traditional clinical settings.³ Indeed, SSIs can successfully treat youth psychopathology: In a meta-analysis of 50 randomized controlled trials, SSIs reduced youth mental health difficulties of multiple types (mean $g=0.32$).³ To date, one SSI has been shown to reduce youth depressive symptoms in multiple RCTs: the online “growth mindset” (GM) SSI, which teaches the belief that personal traits are malleable rather than fixed.⁴⁻⁸ As one example, a 30-minute GM-SSI led to significant 9-month MD symptom reductions in high-symptom youths ages 12-15 versus a supportive therapy control ($N=96$; $ds=0.60$, 0.32 per parent and youth reports).⁶ Thus, GM SSIs represents a scalable, evidence-based strategy for reducing youth depressive symptoms.

GM-SSIs can also strengthen parent beliefs about the effectiveness of mental health treatment, which robustly predict whether youths ultimately access services.⁹ A recent RCT including 430 parents of youth ages 7-17 indicated that an online, 15-minute SSI teaching growth mindset of emotion (viewing

emotions as malleable) significantly increased parents' beliefs that psychotherapy could be effective, both for themselves ($d=0.51$) and their offspring ($d=0.43$), versus a psychoeducation control.⁶ By helping reverse parents' low expectancies for treatment, this low-cost program may enhance parents' odds of seeking services for children with mental health needs.

Accordingly, this study will test whether empirically-supported GM-SSIs can help bridge the gap between PC-based depression screening and access to depression services for high-symptom youth. Youths reporting elevated internalizing symptoms at a PC visit will be randomly assigned to one of two conditions: Information, Psychoeducation, and Referral (IPR; i.e., usual care) or IPR enhanced with youth- and parent-directed online SSIs (IPR+SSI), designed to reduce youth internalizing symptoms and improve parents' mental health treatment expectancies, respectively. We predict that (1) IPR+SSI will increase parents' treatment-seeking behaviors, versus IPR alone, across 3-month follow-up; (2) IPR+SSI will reduce youth depressive symptoms across 3-month follow-up versus IPR alone; (3) IPR+SSI will reduce parental stress and psychological distress across 3-month follow-up, versus IPR alone; (4) parents and youths will rate this service delivery model as acceptable.

Method Summary (see *Figure 1*). Per youth-reported internalizing symptom elevations during a PC visit (score ≥ 5 on the Pediatric Symptom Checklist internalizing subscale), eligible families ($N=246$; youth ages 11-16) will be invited to participate in the study. In online surveys, parents will self-report recent treatment-seeking behaviors, expectancies for psychotherapy, stress and psychological symptoms, and youth mental health problems, along with family and demographic information; youths will self-report symptom levels. Within the same survey, youths and parents will then be randomized (1:1 allocation ratio) to one of two experimental conditions (IPR+SSI or IPR alone); those assigned to IPR+SSI will complete an intervention feedback form immediately post-intervention. At 3-month follow-up, to assess SSI effects on parent treatment-seeking, parent stress and symptoms, and youth depressive symptoms, participating youths and parents will complete the same questionnaires administered at baseline.


Promoting treatment access following pediatric primary care depression screening: Randomized trial of web-based, single-session interventions for parents and youths

Psychiatric disorders are the leading cause of disability worldwide, and 40.5% of this burden is attributable to major depression.¹ Depression symptoms and disorders increase markedly in adolescence, with nearly 20% of youth experiencing depression between ages 11 and 18.² Despite this early onset and protracted course, up to 70% of U.S. youth with depression never receive services.^{2,3} To improve identification of youths in need of services, the American Academy of Pediatrics released practice guidelines promoting depression screening in primary care (PC) clinics.⁴ However, even when identified by PC providers and offered community referrals, <50% of youth with depressive symptoms access treatment.⁴ Thus, there is a need for interventions that are feasible for families to access and complete; can be offered via PC clinics efficiently and cost-effectively; and that encourage parents to seek out services for offspring in the future.

Single-session interventions (SSIs) may forward these goals. SSIs include core elements of comprehensive evidence-based treatments, but their brevity makes them easier to disseminate.^{5,6} Indeed, SSIs can successfully treat youth psychopathology: In a meta-analysis of 50 RCTs, SSIs reduced youth psychiatric difficulties of multiple types (mean $g=0.32$), including web-based SSIs (mean $g=0.32$).⁵ To date, one SSI has reduced youth depressive symptoms across multiple trials: the growth mindset (GM)-SSI, which teaches the belief that traits and attributes—such as sadness, shyness, and loneliness—are malleable rather than fixed.⁷⁻⁹ A web-based, 30-minute GM-SSI has led to significant 9-month depressive symptom reductions in high-symptom youth ages 12-15, versus a supportive-therapy SSI ($N=96$; $ds=0.60$, 0.32 per parent and youth reports, respectively).¹⁰ Separately, a GM-SSI significantly reduced depressive symptoms across 4 months in adolescent girls ($N=222$; $d=0.23$), versus an active control.⁹ Thus, the GM-SSI may be a scalable, promising strategy for reducing youth depressive symptoms.

GM-SSIs may also strengthen parent *beliefs* about the effectiveness of mental health treatment, which robustly predict whether youths ultimately access and benefit from services.¹¹ In a RCT of 430 parents of youth ages 7-17, an online, 15-minute SSI teaching growth emotion mindset (viewing emotions

as malleable) significantly increased parents' beliefs that psychotherapy could benefit themselves ($d=0.51$) and their children ($d=0.43$) versus a psychoeducation control.¹² This low-cost, self-administered program may improve parents' treatment expectancies, potentially improving their likelihood of seeking support for their children's mental health needs.

Present study. We will examine whether these online GM-SSIs can bridge the gap between PC-based depression screening and service access for high-symptom youth. Youths ages 11-16 ($N=246$) reporting elevated internalizing symptoms at a PC visit will receive either Information, Psychoeducation, and Referral (IPR; usual care) or IPR enhanced with youth- and parent-directed online GM-SSIs (IPR+SSI), designed to *reduce youth depressive symptoms* and *improve parents' expectancies of mental health treatment*, respectively. Our primary hypotheses are two-fold. We predict that (1) IPR+SSI will increase parents' treatment-seeking behaviors, versus IPR alone, across 3-month follow-up; and we predict that (2) IPR+SSI will reduce youth internalizing symptoms across 3-month follow-up versus IPR alone. Hypotheses (1) and (2) are co-primary outcomes; both will help gauge whether GM-SSIs improve access to effective treatment, either as stand-alone interventions or by promoting increased service-seeking.

We expect that these co-primary hypotheses may relate to one another in at least two ways, although we do not have specific predictions as to how this interrelation may manifest (see *Figure 2*). First, the SSIs' effects on parent treatment-seeking and youth internalizing symptoms may relate *inversely* to one another, due to *differential* intervention effects on each outcomes. That is, the SSIs might positively influence youth problems *or* parent treatment-seeking, depending on which effects are more rapidly apparent to the family. For instance, if effects on youth internalizing symptoms emerge more rapidly and overtly than effects on parent treatment-seeking, parents may in turn be less inclined to seek additional care. Likewise, if effects on youth symptoms fail to emerge within a short period of time, parents may be *more* inclined to seek additional care after completing the parent-directed SSI. Thus, is it possible that effects may emerge for *either* parent treatment-seeking *or* youth symptoms, but not both. Conversely, it is possible that the SSIs may positively affect parent treatment-seeking and youth

internalizing symptoms *simultaneously*. If parents perceive initial symptom reductions in their child following the SSI, these initial improvements—indicating the potential for further gains—may *further* motivate them to seek additional care. We perceive both pattern of results as equally plausible in the present trial; either would help clarify the potential role(s) of these SSIs within pediatric primary care.

In addition to our co-primary hypotheses, we will also test two secondary hypotheses to further contextualize the intervention's effects and acceptability. We predict that (3) IPR+SSI will reduce parental stress and psychological distress across 3-month follow-up, versus IPR alone, and (4) families will rate this service delivery model as acceptable.

Method

Study Design. This study will be a two-arm randomized-controlled trial with 1 active intervention condition and 1 active control condition (1:1 allocation ratio). Procedures were pre-registered on ClinicalTrials.gov on 7/24/2019 (NCT04030897; anticipated date of first enrollment: 12/15/2019). The University Institutional Review Board (#IRB2019-00241) approved all study procedures on 7/8/2019. Project funding is provided by the Klingenstein Third Generation Foundation.

Youths and parents will complete all study procedures remotely via personal internet-equipped devices. After discussing procedures with a research team member via telephone, eligible families will receive a study link from which parents and youths may provide consent and assent and complete their respective study portions. In separate Qualtrics-based surveys, parents and youths will complete baseline questionnaires, the GM-SSIs (or 'waitlist' notification; IPR will be provided to all families at initial PC appointments), and post-intervention questionnaires within a single online survey lasting approximately one hour per family member. Parent-youth pairs will both be assigned to the same condition (GM-SSI or 'waitlist') via survey-embedded random-number generators; randomization will not be stratified. Subsequently, three-month follow-up questionnaires will be administered via Qualtrics-based surveys. Follow-up surveys will assess parents' treatment-seeking behaviors, youth symptoms, parental stress and psychopathology, and related variables (detailed below). Families who do not complete follow-up surveys

within 3 days of contact will receive ≤ 3 reminder messages. After completion of the 3-month follow-up, families who did not initially receive GM-SSIs will be granted intervention access.

Participants and Recruitment. We will recruit two-hundred youths ages 11-16 and one parent per youth from nine community-based branches of the University Hospital's Pediatric Primary Care service. Per the University Medical Center's policies, providers at all sites administer the youth-report Pediatric Symptom Checklist (PSC)¹³ to patients 11 and older. Providers review patients' PSC scores during their appointments; all youths reporting symptom elevations receive an "Information, Psychoeducation, and Referral" folder, including contact information for local mental health providers and psychoeducational materials. In this study, youths with an elevated PSC-Internalizing Score (5/10 or higher, per 0-2 ratings of five items: *Feel sad or unhappy, feel hopeless, down on yourself, seem to be having less fun, worries a lot*) may be eligible for participation, per existing PSC-Internalizing cut-offs.¹⁴ Because the PSC is already implemented and scored across participating clinics, and because PSC scores are used to direct distribution of "Information, Psychoeducation, and Referral" resource folders to patients, using the PSC as an eligibility screen creates no added clinical burden for providers. Within 3 weeks of the youth's PC appointment, a research team member will contact potentially eligible families by phone to introduce the study and invite them to participate. Additional inclusion criteria, assessed during this call, include English-language proficiency and comfort completing computer-based activities. Receipt of mental health services upon enrollment will be monitored but will not preclude participation.

The parent- and youth-directed interventions last approximately 15-30 minutes. Thus, there is no plan to discontinue interventions due to worsening symptoms, but participants will be informed that they may stop participating in the study at any time without penalty.

Sample size justification. First, using G*Power 3.1, we calculated samples needed to achieve 80% power to detect a small (per Cohen's recommendations: $d=.2$ or $OR=1.49$), medium ($d=.5$ or $OR=3.45$), and large effects ($d=.8$ or $OR=9.00$) effect on primary outcomes (parent treatment-seeking behaviors, per logistic regression, and youth depressive symptoms, per linear regression) at $\alpha=.05$ for a two-arm RCT, including two covariates (baseline youth depression symptom severity; intervention

condition). *N*s were 392, 55, and 25, respectively, for a regression predicting, and 615, 89, and 50, respectively, for a logistic regression predicting parent treatment-seeking behaviors at 3-month follow-up. However, it is necessary in this study to consider our multisite recruitment structure (9 sites total). GM-SSIs have previously produced small-to-medium improvements in youth depressive symptoms and parent treatment expectancies; we thus used procedures outlined by Feaster, Mukulich-Gilbertson, and Brincks¹⁵ to obtain more precise power estimates for a mixed-effects model predicting medium up ($d = 0.5$) changes in youth depressive symptom severity from baseline to 3-month follow-up, assuming low variability in treatment across sites (0.05). A target *N* of 246 (approximately 26-28 youths per site, although we cannot accurately project exact site-specific recruitment totals in advance) would ensure 92% power to detect an average intervention effect of $d = 0.5$ and 80% power to detect a minimum average effect size of $d = 0.42$. As such, a target *N* of 246 was selected for this study. Notably, participants will be randomized at the study level—not at the site level—ensuring an even number of families assigned to both study conditions overall.

Intervention Descriptions

Youth-Directed Growth Mindset (GM) SSI.¹⁰ The web-based, youth-directed GM-SSI is delivered via Qualtrics and is approximately 30 minutes long. All activities are self-administered and delivered in a web-based format, including illustrations, graphics, and audio-recordings. Content is designed to maximize relevance for youths experiencing depressive symptoms (e.g., sadness, hopelessness) and includes five components: 1. A brief lesson on neuroplasticity, describing how behaviors are controlled by thoughts and feelings in the brain, and thus have potential for change; 2. Stories from older youths describing beliefs that their traits (e.g., sadness, anxiety) are malleable; 3. Further stories by older youths, describing times when they applied this knowledge to cope with emotional setbacks; 4. Scientific studies suggesting that personality can positively change over time; and 5. An exercise in which participants write notes to younger peers, using newly-gleaned knowledge to generate advice on coping with an emotional setback. Here, youths are presented with a hypothetical peer rejection scenario and respond to the following prompt: “How do you think you would feel if this

happened to you? What kinds of thoughts do you think you would have?” Next, youths are asked to “imagine that the same event you just wrote about happened to another kid just like you. What could you say to help them understand that they can change, or things that are happening to them could change?”

Parent-Directed Growth Mindset (GM) SSI.¹² The web-based, parent-directed GM-SSI takes 15 minutes. Parents first read a brief passage, “Can We Change Our Emotions?” presenting data, quotations, and examples conveying the argument that emotions are inherently flexible in youths and adults. Parents then read another passage, “Is Failure a Friend or Foe?” illustrating the notion that failure promotes learning, growth, and self-reflection. After each passage, parents are asked to write a brief summary of its main arguments “as though you were trying to convince a fellow parent why the passage’s main arguments are true.” This exercise is designed to promote internalization of the passage’s ideas.

To assess program completion, user-activity tracking markers will be embedded into our Qualtrics surveys for participants.

Information, Psychoeducation and Referral (IPR). IPR represents usual care in the University Hospital’s Pediatric Primary Care Division; it is routine practice at all clinics in this study. All families of youths with elevated depressive symptoms during a PC visit receive a folder containing informational materials about the nature of depression and referrals to providers in their area. All families in this study will have received PC-based IPR before enrollment, per University Medical Center policy.

Potential bias sources. Families will know whether they receive GM-SSIs immediately or after follow-up. To minimize other potential performance bias sources, families will be randomized remotely via online surveys; thus, the research team and PC providers will be blinded to condition. Second, some eligible families may have limited computer access, creating possible selection bias. We therefore designed study questionnaires and interventions to be completable on *any* internet-equipped device (smartphones, tablets, computers). Additionally, if an eligible youth with limited internet access is interested in participating in the study, research team members will work with the family to identify local venues where internet-equipped devices are accessible (e.g., public libraries/community centers).

Trial conduct. Data will be monitored on an ongoing basis (daily) for quality assurance purposes and to ensure protocol compliance. Further, we will follow University IRB policies for expedited adverse event (AE) reporting. The PI will review data for potential AEs in real-time throughout the trial; AEs occurring during the study will be reported to the IRB within 48 hours. Any protocol alterations that become necessary will be approved by the IRB before implementation.

Data confidentiality and sharing statement. Data will be collected via Qualtrics and stored on password-protected electronic servers meeting University security standards. After the funding period concludes, de-identified participant-level data will be posted publicly via Open Science Framework (OSF). Intervention materials are available from the first author upon request.

Measures (see **Table 1** for SPIRIT information).

Mental Health Treatment-Seeking Checklist (Co-Primary Outcome). At baseline and 3-month follow-up, parents will indicate their engagement ('yes'/'no') in four treatment-seeking behaviors for their child: researched local mental healthcare providers/agencies; contacted mental healthcare provider or agency about treatment; contacted child's school regarding mental health supports; and scheduled an appointment *or* placed child on waiting-list with a mental healthcare provider/agency (number of treatment-seeking behaviors ranges from 0-4). At baseline, parents will report whether they engaged in these behaviors since the child's PC appointment, and at follow-up, since their last survey. Parent treatment-seeking will be a primary outcome.

Children's Depression Inventory-2 (CDI-2; Co-Primary Outcome). Parents and youths will complete the CDI-2 scale at baseline (pre-intervention) and 3-month follow-up. The CDI-2 is a reliable, valid measure of youth depression severity, normed for youth age and sex and yielding raw and T scores, along with an index of functional impairment. The CDI-2 is highly sensitive to clinical change across treatment and is used routinely in clinical trials for treating youth depression.^{3,7,10} Change in self-reported youth depressive symptoms will be a primary outcome; parent-reported youth depression symptoms is a secondary outcome.

Pediatric Symptom Checklist (PSC; Eligibility screener and secondary outcome). The PSC is a widely-used, validated measure of overall youth psychopathology, including internalizing, externalizing, attention, and total symptoms, based on 35 items rated 0-2.¹⁵ Because participating clinics administer the PSC during all PC visits, the PSC will serve as the study's eligibility screener. Youth depressive symptoms will be indexed via the 5-item PSC Internalizing Subscale (score range 0-10).¹⁶ A score of ≥ 5 will indicate possible trial eligibility. Receiver operating characteristics analyses suggest that the PSC-17 Internalizing subscale performs as well as competing screens (e.g., the Children's Depression Inventory and Child Behavior Checklist) in predicting depression diagnoses based on clinical interviews (AUC >0.80).¹⁶ Youths and parents will also complete the full PSC-17 at baseline and follow-up; changes in overall youth- and parent-reported youth psychopathology will be secondary outcomes.

Beck Hopelessness Scale-Short Version (BHS-4). The BHS-4¹⁸ is a valid, reliable 4-item version of the 20-item BHS¹⁹ assessing hopelessness in youths and adults.^{20,21} Parent and youth self-reported hopelessness will be assessed at baseline, post-intervention (if assigned to the IPR+SSI group), and follow-up. Higher sum-scores (range: 0-12) reflect greater hopelessness.

Brief Symptom Inventory-18 (BSI-18). The BSI-18 is a reliable, validated measure of self-reported psychopathology and distress.^{22,23} At baseline and 3-month follow-up, parents will rate endorsement of 18 physical and emotional complaints from 0-4. Sum scores yield a total distress score (range: 0-72).

Barriers to Accessing Care Evaluation (BACE). The BACE is a well-validated assessment of the degree to which beliefs, concerns, and circumstances have stopped or discouraged individuals from accessing youth mental health services.²⁴⁻²⁶ At baseline and follow-up, parents will rate its 30 items on a 0-3 scale. Higher scores (range: 0-90) indicate greater service access barriers.

Attitudes Toward Therapy Scale. This single-item scale assesses parents' perceptions that therapy/counseling would help reduce their child's mental health difficulties.¹² At baseline, post-intervention (if assigned to IPR+SSI), and 3-month follow-up, parents will rate the item from 0-10. Higher scores indicate stronger beliefs that therapy may help reduce mental health problems.

Mental Health Treatment Access. Parents will indicate (yes/no) whether their child has received (a) new and/or (b) continuing school-based, outpatient, or other mental health-related services since the child's recent PC appointment (at baseline) and since the baseline assessment (at follow-up).

Perceived Stress Scale. The PSS is a validated measure of one's appraisal of daily life as stressful, unpredictable, and uncontrollable.^{27,28} At baseline and follow-up, parents will rate 10 items from 0-4, with higher scores indicating greater perceived stress (range: 0-40).

Implicit Theories of Emotion Scale. The ITE Scale^{29,30} will serve as a manipulation check for the parent-directed GM-SSI. At baseline and post-intervention (IPR+SSI group only), parents will report the degree to which they view emotions as malleable (versus immutable) on a 1-6 scale across four items. Higher mean scores (range: 1-6) indicate stronger fixed emotion mindset, and lower scores, stronger growth emotion mindset.

Implicit Theories of Personality Questionnaire. The ITPQ³¹ will be used as a manipulation check for the youth-directed GM-SSI. At baseline and post-intervention (IPR+SSI group only), youths will rate agreement with three statements linked to malleability of personality. Higher mean scores indicate stronger fixed personality mindsets, and lower scores, stronger growth personality mindsets (range: 1-6).

Intervention Feedback Scale. Immediately post-intervention, the Intervention Feedback Scale³² will ask youth and parents receiving GM-SSIs to indicate how much they enjoyed, understood, felt helped by, would recommend, and agreed with the program's message. They will also be prompted to provide written feedback regarding their impressions of the program.

Adverse Childhood Experiences (ACEs). The ACEs questionnaire is a well-validated measure of exposure to violence, childhood emotional, physical, or sexual abuse, and household dysfunction during childhood.^{33,34} Parents will complete the ACEs questionnaire at baseline in reference to their child and to themselves.¹

¹ We do not plan to use the ACEs questionnaire in primary study analyses. Rather, we are including this questionnaire to allow for future tests of whether trauma exposure influences GM-SSI intervention

Demographics. Parents will report family and background information (e.g. youth age, sex, mental health treatment history).

Analytic Plan

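### Recruitment text gives 200 youths against a selected target of 246, and the 92%/80% power for youth symptoms ignores the plan's FDR rule and missing follow-up, so it is not assured

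*Combined protocol and SAP*

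**What the plan says.** **Sample size.** Participants and Recruitment: "We will recruit two-hundred youths ages 11-16 and one parent per youth from nine community-based branches". The other places differ. The synopsis (Method Summary) has "eligible families ($N=246$; youth ages 11-16) will be invited to participate in the study". Present study has "Youths ages 11-16 ($N=246$) reporting elevated internalizing symptoms at a PC visit". Sample size justification concludes that a target "of 246 was selected for this study", described as "approximately 26-28 youths per site". Study timeline says recruitment continues until the target is reached.

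**Power.** For H2 (youth self-reported depressive symptoms), Sample size justification says 246 "would ensure 92% power to detect an average intervention effect of $d = 0.5$ and 80% power" at a minimum average d of 0.42. It assumes nine sites and low between-site variability in the treatment effect, given as 0.05. The only alpha in that section is .05, in the preceding G*Power step. No loss to follow-up is stated.

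**Decision rule.** Correction for multiple tests calls a result significant only if its Benjamini-Hochberg (BH) q-value is below 0.05, computed over all pre-registered tests of H1 to H4. Missing data provides for subject-level missingness through maximum likelihood and multiple imputation, without an expected rate.

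**The concern.** There are two issues of different weight.

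First, a reader cannot tell from Participants and Recruitment alone when enrolment ends, because recruitment stops at the target and that section gives a different number from the one the power rests on.

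Second, the power sentence promises an outcome ("would ensure") under conditions that differ from those of the analysis. BH at q < 0.05 is never looser than p < .05, so under otherwise equal assumptions H2 power can only fall. Missing three-month outcomes lower it further. If the shortfall is material, a null H2 result would be read against a power figure that the test did not have.

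**Working it through.** **1. Which sample size.** Nine sites at 26-28 give 9 × 26 = 234 to 9 × 28 = 252. 246/9 = 27.3 lies inside the per-site range; 200/9 = 22.2 does not. 246 appears in three places and is the one described as selected.

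**2. Reproducing the stated power.** Inputs from Sample size justification: N = 246, 9 sites, 0.05 read as the variance of the standardised site effects. Assumed: two-sided alpha .05, normal test, all 246 analysed, baseline correlation r = 0.

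SE = sqrt((0.05 + 4(1 − r²)/(N/9))/9) = sqrt((0.05 + 4/27.33)/9) = 0.1477

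Power = Φ(d/SE − 1.96)

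- d = 0.5: Φ(3.385 − 1.96) = 92.3% (stated 92%)
- d = 0.42: Φ(2.844 − 1.96) = 81.2% (stated 80%)

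Reading 0.05 as an SD (variance 0.0025) with a t reference on 8 df gives 92.4% and 81.5%, so the stated figures do not settle which was meant. The steps below use the variance reading.

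**3. Size of the FDR family.** H1 has two models (linear and logistic), H2 one, H3 two: five. The parent-report CDI-2 model would make six. It is called secondary, and Table 1 shows no three-month parent CDI-2 although the Measures text does. H4 is judged descriptively. The strictest BH step is .05/5 = .01 or .05/6 = .0083.

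**4. H2 power under BH, 246 analysed.** Simulation with 400,000 draws, independent tests, every real effect equal to d, the same SE for each test. Ranges cover five and six tests.

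| Which effects are real (r = 0) | d = 0.5 | d = 0.42 |
|---|---|---|
| All | 92% | 79% |
| All except the two H1 tests | 88-89% | 72-73% |
| Only H2 | 78-80% | 59-61% |

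**5. Missing follow-up, alpha .05, r = 0.** An assumed 20% loss leaves 197. SE = sqrt((0.05 + 4/21.89)/9) = 0.1608, giving 87.5% and 74.3%. An assumed 10% loss gives 90.2% and 78.0%.

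**6. If d is unadjusted and baseline predicts follow-up.** The H2 model adjusts for baseline, but the plan gives no correlation.

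- r = 0.4, 197 analysed, alpha .05: 91.4% and 79.8%.
- r = 0.5, 246 analysed, BH, d = 0.42: about 87% if all effects are real, about 83% if only H1 is null, 70-72% if only H2 is real.

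**The case against.** The arithmetic in Sample size justification is sound on its own terms, and that section never says the power allows for FDR or attrition. The 200 has one evident correction. Both points stand. They make this a matter of consistency and labelling, not a failed calculation.

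Three stronger readings are tempting, and the documents do not support them.

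- *That the stated power holds only with 246 analysed at alpha .05.* Step 6 shows otherwise: a moderate baseline correlation can bring power back to about the stated level or above it, under BH or with 20% loss.
- *That H2 power falls by 16 to 33 points, or to about 48%.* The fall of that size needs every other test to be null. Present study says only that "effects may emerge for *either* parent treatment-seeking *or* youth symptoms, but not both". That either/or does not extend to the H3 outcomes or to parent-reported symptoms, and the plan predicts H3 effects. The 48% also stacks the SD reading, a t test on 8 df, six tests and r = 0. The plan does not specify the degrees of freedom.
- *That the trial may really be planned at 200, or needs more families.* Three sections and the per-site figures point to 246, and nothing above shows that 246 is inadequate.

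The meaning of 0.05 may be defined in the cited multisite methods paper, which was not available for this review. That weakens any criticism of the parameter but not the request to state it.

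**Conclusion.** The concern holds in two parts. The 200 contradicts the selected 246; this needs no assumption. The 92%/80% describes an unadjusted alpha .05 test with complete follow-up, which is not the rule or the data that the Analytic Plan expects.

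On the plan's own inputs the consequence at d = 0.42 ranges from small (about 79% under BH if all effects are real) through moderate (72-73% if H1 is null, a pattern Present study treats as plausible) to about 60% if H2 alone is real. The sizes rest on assumptions not in the documents: independent tests, equal real effects, the variance reading of 0.05, the loss rate and r. Because a favourable r could offset some or all of the loss, the supportable conclusion is that 246 does not *ensure* the stated power, not that the trial will miss it. No power is stated for H1 at 246, and nothing here bears on it.

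**What to change.** 1. In Participants and Recruitment, change 200 to 246.
2. In Sample size justification, do one of the following:
   - label 92%/80% as power at unadjusted two-sided alpha .05 with complete follow-up; or
   - recompute H2 power for the number expected to be analysed, and report it as a range from alpha .05 to the strictest BH step (.01 for five tests, .0083 for six). State the expected three-month loss, whether 0.05 is a variance or an SD, whether d is baseline-adjusted (with the assumed correlation if not), and whether the parent-report CDI-2 model is in the FDR family.

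The values above illustrate the size of the issue and are not replacement text. The cost is wording and at most one recalculation, with a less favourable stated power as the downside. The design, analysis and enrolment target stay as they are.
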